6.5. Visit Windows

By-visit analysis (including efficacy, laboratory data, vital signs, ECG, ADA) will be summarized by the nominal visit number and no visit window will be defined. Assessments taken outside of protocol allowable windows will be displayed according to the case report form (CRF) assessment recorded by the investigator. For assessments without a nominal visit number such as EOT and EOS assessments, a visit number will be assigned based on the actual visit date using the study day and visit window as in [Appendix 10.2 Table 1](#) Schedule of Events.

The following visit windows will be used to map the unscheduled visits, early end of treatment visits, early study termination visits and daily electronic dairy entries, based on the study day:

Visit No.	Visit	Targeted Study Days*	Analysis Window in Study Days
1	Screening	Day -37 to day -8	≤8
2	Pre-randomization	Day -7 to -4	-7 to -3
3	Baseline	1	1
4	Week 2	15	[12,18]

5	Week 4	29	[22, 36]
6	Week 8	57	[50, 64]
7	Week 12	85	[78, 92]
8	Week 16 (End of Treatment)	113	[106, 120]
9	Week 20	141	[134, 148]
10	Week 36 (End of Study)	253	[246,260]

*Study days are calculated from the first administration of study drug (Day 1)

If multiple measurements occur within the same analysis window, the following rules will be used to determine the analysis value:

- When multiple valid measurements occur within the same analysis window, the closest to the target study day will be used in the analysis.
- When multiple valid measurements occur within equal distance from the target study day, the value after the target study day will be used in the analysis.

Both scheduled and unscheduled measurements will be considered for determining abnormal/PCSV values from laboratory, vital sign or ECG as well as the baseline values.

6.6. Unscheduled Assessments

The determination of baselines and values at the end of treatment for both efficacy and safety variables will be based on available assessments of scheduled and unscheduled visits. For by visit summaries, only scheduled assessments are included.

6.7. Pooling of Centers for Statistical Analyses

There is no pooling of centers planned for the statistical analysis.

7. INTERIM ANALYSIS

An administrative interim analysis may be conducted by a team of independent statisticians and programmers. The results of this interim analysis will be used to make appropriate business decisions.

Since the time that dosing was stopped in this study, two unblinded interim analysis of efficacy have been conducted. The first unblinded interim analysis was conducted immediately after being placed on clinical hold and the second was conducted at the time when the last patient who received study drug before the trial was placed on clinical hold would have completed the 16week time point.

No new or unexpected safety signals were observed.

The conduct of these administrative interim analyses was performed by independent personnel not involved with the conduct of the study. Regeneron personnel directly involved in the conduct of the study including study medical monitor and biostatistician remain blinded at the subject level.

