5.5.1. Blinding

Study patients, the principal investigators, and study site personnel will remain blinded to all randomization assignments throughout the study. The Regeneron study medical director, study monitor, and any other Regeneron and contract research organization (CRO) personnel who are in regular contact with the study site will remain blinded to all patient randomization assignments.

Blinded study drug kits coded with a medication numbering system will be used. In order to maintain the blind, lists linking these codes with product lot numbers will not be accessible to individuals involved in study conduct.

Anti-drug antibody (ADA) results will not be communicated to the sites before the end of the study, and the sponsor operational team will not have access to results associated with patient identification until after the final database lock.

One administrative interim analysis may be conducted. No study personnel involved in the day-to-day conduct of the study will have access to unblinded data before the database is locked for this study.

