9.5.6. Interim Analysis

An administrative analysis may be conducted by a team of independent statisticians and programmers. The administrative analysis may include an assessment of drug concentrations. The results of this interim analysis will be used to make appropriate business decisions. There is no intention to stop the study early or to modify the conduct of the study based upon this information. The results will only be reviewed by Regeneron Senior Management and other personnel not directly involved with the conduct of the study.

Detailed interim analysis timing and analyses will be prespecified in the SAP.

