1. OVERVIEW

This Statistical Analysis Plan (SAP) is intended to be a detailed description (expanding on the statistical analyses described in the protocol) of the definitions and statistical techniques to be used for the analyses of data collected in the R475-PN-1524 study. This SAP will be finalized prior to database lock to ensure the credibility of the study results by pre-specifying the statistical methods for the data analyses before unblinding of treatment assignments.

This plan may be revised during the study to accommodate protocol amendments and adapt to unexpected issues in study execution that may affect planned analyses.

Background/Rationale

This randomized, double-blind, multi-dose, placebo-controlled study is designed to evaluate the safety and efficacy of fasinumab in patients with moderate to severe chronic non-radicular LBP who have a history of intolerance or inadequate pain relief from paracetamol/acetaminophen and at least one oral NSAID and at least one opioid. This subset of patients with chronic LBP represents a patient population with an unmet medical need in whom it would be appropriate to prospectively study the hypothesis that fasinumab provides benefit and has an acceptable safety profile.

Dose selection for this multiple-dose study in patients with chronic non-radicular LBP is based on data from 2 completed fasinumab phase 1 studies in healthy subjects (studies R475-PN-0817 and TDU-11480), as well as data from the completed fasinumab phase 2 proof-of-concept study in patients with pain due to OA of the knee (study R475-PN-0901), and the single-dose proof-of-concept study in patients with sciatic pain (study R475-PN-0908), the dose-range evaluated in an ongoing fasinumab phase 2 study in patients with OA of the knee or hip (study R475-PN-1227), and pharmacokinetic (PK) simulations.

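### The SAP text post-dates two unblinded efficacy looks, changes the protocol's primary analysis without listing the changes, and still says its methods were set before unblinding.

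*SAP*

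**What the plan says.** **Interim analyses.** Protocol 5.5.1 states: "One administrative interim analysis may be conducted". It adds: "No study personnel involved in the day-to-day conduct of the study will have access to unblinded data before the database is locked". Protocol 9.5.6 describes an administrative analysis for business decisions, with results going only to senior management and others not directly involved in conduct. It ends: "Detailed interim analysis timing and analyses will be prespecified in the SAP".

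SAP Section 7 opens with a single administrative interim analysis that may be conducted. It then reports that "two unblinded interim analysis of efficacy have been conducted": one immediately after the clinical hold, and one when the last patient dosed before the hold would have reached week 16. It says that independent personnel not involved in study conduct performed them, and that sponsor staff directly involved in conduct, "including study medical monitor and biostatistician remain blinded at the subject level".

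**Prespecification.** SAP Section 1 describes its purpose as "pre-specifying the statistical methods for the data analyses before unblinding of treatment assignments". SAP 1.1.5, the place for modifications from the protocol's statistical section, says only that the SAP is based on Amendment 3. SAP 1.1.6, the revision history, says there are none.

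**Reason for change.** The background in SAP Section 1 describes the partial clinical hold, the early end of dosing and 563 patients randomized at that time. It says that the planned analyses take this into account.

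**The concern.** A prespecified analysis is credible because it was fixed when nobody choosing it could know which version favours the drug. Here the only recorded SAP describes two by-arm efficacy looks as past events. That same text contains a primary analysis different from the protocol's. The second look was timed so that week 16 pain scores could have been available for essentially every dosed patient, although the SAP gives no data cut or completeness figure.

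Keeping patient-level codes hidden does not settle the matter, because group-level results are enough to tell which analysis looks better. SAP Section 7 is silent on group-level access for those who wrote, approved or programmed the plan. With SAP 1.1.5 blank on the departures and SAP 1 asserting prespecification before unblinding, a reader of the study report would take the unadjusted mITT p-values as fixed before any look. The documents do not support that.

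**Working it through.** **1. Order of events.** SAP Section 7 uses the past tense for both looks, so that text was written after them. SAP 1.1.6 records no amendment, so no earlier SAP is on record. Looks allowed by Protocol 5.5.1: 1. Looks done: 2. Protocol 9.5.6 required timing and content to be set in advance in the SAP; the SAP reports the timing afterwards and gives no content beyond efficacy.

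**2. What the protocol had fixed and what the SAP changed.**

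| Item | Protocol | SAP |
|---|---|---|
| Endpoint | Week 16 change in average daily LBPI NRS (8.2) | Same (4.4.1) |
| Model | MMRM; strata, baseline, treatment, visit, interaction; no imputation (9.5.2.1) | Same terms (5.7.1) |
| Primary set | FAS (9.3.1) | mITT, at least one dose (3.1, 5.7.1) |
| Data span | All data to week 16, including after stopping treatment (9.5.2.1) | Earlier of consent withdrawal, week 16, or 5 weeks after last dose (5.7.1) |
| Multiplicity | Hochberg on two SC doses, then gate to IV (9.1) | None (5.7.1) |
| Pattern-mixture sensitivity analysis | Yes (9.5.2.1) | Absent |
| Per-protocol sensitivity analysis | Yes (9.3.3, 9.5.2.1) | Absent; no such set in Section 3 |
| FAS analysis | Primary | Sensitivity (3.2, 5.7.1) |

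The last five changes to the planned analysis, together with the new set, are the departures. SAP 1.1.5 lists none.

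**3. Where the 5-week cut acts.** Last dose at week 12: 12 + 5 = week 17, so week 16 data stay in. Last dose at week 8: 8 + 5 = week 13, so week 16 data drop out. The cut therefore acts on patients whose dosing ended early, including those stopped by the hold. Their number is not given.

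**4. Size of the multiplicity change.** Assume three active arms of equal size against a shared placebo, no true effect anywhere, and Z_i = (X_i − X_0)/√2 with standard normal X, so pairwise correlation is 0.5.

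- Protocol procedure: P(max(p1, p2) ≤ 0.05 or min(p1, p2) ≤ 0.025). The IV test follows only if both SC hypotheses are rejected, so it adds no first error here. Result: **4.8%**, consistent with the protocol's stated study-wise level of 0.05.
- SAP: P(any of three |Z_i| > 1.96), by numerical integration: **12.5%** (a one-million-draw simulation gave 12.4%). If the three tests were independent: 1 − 0.95³ = 14.3%.
- Ratio: 12.5 / 4.8 = 2.6.

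**5. Size of a free choice of analysis (illustration only).** For one comparison under the null, taking the better of two analyses gives P(|U| > 1.96 or |V| > 1.96). The correlation between the two statistics is not in the documents, so a range is assumed.

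| Assumed correlation | Type I error |
|---|---|
| 0.95 | 6.5% |
| 0.90 | 7.0% |
| 0.80 | 7.8% |
| 0.70 | 8.3% |

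This is what would be at risk if a choice had been made with results known. It is not an estimate of what happened.

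**The case against.** Much can be said for the sponsor, and most of it stands.

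- **The core of the primary analysis came first.** A reader might infer that the primary methods as a whole were fixed after the looks. They were not: the endpoint, MMRM, covariates, no-imputation rule, full analysis set and multiplicity procedure are all in the protocol. Only the departures first appear in the later text.
- **No breach of the blinding rule is shown.** A reader might take blinding at the subject level as an admission that the team knew group results. Protocol 5.5.1 restricts personnel in day-to-day conduct, Protocol 9.5.6 lets senior management see results, and SAP Section 7 says independent personnel did the work. Silence on group-level access is a gap, not evidence of access.
- **The safety sentence proves little.** "No new or unexpected safety signals were observed" could suggest that interim output reached the authors. It carries no by-arm efficacy result and does not say which data it rests on.
- **There is a reason unrelated to results.** The hold and the early end of dosing are stated, and both documents allow SAP revision for unexpected events. This plausibly explains the 5-week cut. It does not by itself explain removing multiplicity control or leaving SAP 1.1.5 without a list.
- **Dating is incomplete.** Cover pages are not part of the text reviewed, so the SAP's date is not visible. An empty revision history does not date each choice. First documented after the looks is as far as one can go.
- **Disclosure is partial but real.** SAP Section 7 reports both looks, SAP 5.7.1 openly says there is no multiplicity control, and the FAS analysis is retained.
- **The wording in SAP 1 may refer to the study team's blind only.** If so, the SAP needs to say that.

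**Conclusion.** The point holds in limited form. Three things rest on the documents' own words: two unblinded efficacy looks were done where one was allowed, and they were reported afterwards; the SAP text describing them departs from the protocol's primary analysis and lists no departure; and its statement that methods precede unblinding, read literally, conflicts with its own Section 7.

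The documents do not show that the SAP's authors knew group-level results, or that results shaped any choice. The open question is access, and only the sponsor can answer it.

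The measurable consequence is the loss of multiplicity control: about 4.8% under the protocol's procedure against about 12.5% for three unadjusted tests, under the global null with equal arms and a shared placebo. The 6.5% to 8.3% range for a free choice between two analyses depends on assumed correlations and remains hypothetical. The effect of the 5-week cut cannot be sized, because the number of patients it removes at week 16 is not given.

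**What to change.** 1. **SAP Section 1 and Section 7:** state the order of the SAP and the two looks, with dates. Replace the claim of methods set before unblinding, or confine it to the people for whom it is true. Correct the single-interim wording in Section 7 to two, and acknowledge the departure from Protocol 5.5.1 and 9.5.6.
2. **SAP Section 7:** state whether anyone who wrote, approved or programmed the SAP had access to group-level interim results. If this cannot be established, say so.
3. **SAP 1.1.5:** list each departure (analysis set, data cut, multiplicity control, pattern-mixture and per-protocol sensitivity analyses) as first documented after the looks, with its reason.
4. **SAP 5.7.1:** report the protocol analysis beside the mITT analysis as the result specified before any look: the FAS MMRM with all data to week 16, with Hochberg plus gatekeeping. The SAP says the FAS sensitivity analysis is done the same way as the primary, so state explicitly that the 5-week cut does not apply to it. Do not describe the unadjusted mITT p-values as prespecified before unblinding.

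The cost is small: wording, plus a multiplicity rule applied to an MMRM that is already planned. The downside is that claims from the mITT analysis become weaker. Making the mITT result merely supportive is a further step and a trade-off, since the hold is a fair reason to look at on-treatment data; this point does not require it. The changes should be made before database lock, because they lose most of their value afterwards.

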8. SOFTWARE

All analyses will be done using SAS Version 9.3 or later version if available. .

10. APPENDIX

10.1. Schedule of Time and Events

Table 1 Schedule of Events – Screening and Treatment Periods

Table 1: Schedule of Events – Screening Period Through Week 16

Study Week	Screening Period	Pre-Randomization Period	Treatment						End of Treatment Period	Treatment Period Early Termination Visit
			1	2	4	8	12	16		
Study Day (visit window)	up to -37 to -8	-7 (+3) Pre-Rand Visit	1 Baseline	8 (±1)	15 (±3)	29 (±7)	57 (±7)	85 (±7)	113 (±7)	ET
Visit Number	1	2	3	Ph call 1	4	5	6	7	8	ET
Screening/Baseline:										
Informed Consent	X									
Inclusion/Exclusion	X	X	X							
Genomics sub-study informed consent ¹	X									
Medical History	X									
Medication History	X									
Demographics	X									
Height	X									
Bilateral radiograph of knees, hips and shoulders ²	X									
Lumbar spine MRI ³	X									
MRI of any knee or hip with baseline K-L ≥ 3 ²	X								X	X ⁴
NRS/EDiary training ^{5,7}		X								
Assessment of peripheral or central pain	X									
painDETECT Questionnaire	X									
Randomization			X							
Treatment:										
SC Study Drug Injection ⁶			LOADING DOSE			X	X	X		
IV Study Drug Infusion ⁶			X				X			
Dispense paracetamol/acetaminophen		X	X			X	X	X		
Paracetamol/acetaminophen accountability			X		X	X	X	X	X	X

Study Week	Screening Period	Pre-Randomization Period	Treatment						End of Treatment Period	Treatment Period Early Termination Visit
			1	2	4	8	12	16		
Study Day (visit window)	up to -37 to -8	-7 (+3) Pre-Rand Visit	1 Baseline	8 (±1)	15 (±3)	29 (±7)	57 (±7)	85 (±7)	113 (±7)	ET
Visit Number	1	2	3	Ph call 1	4	5	6	7	8	ET
Concomitant medications	X	X	X	X	X	X	X	X	X	X
Efficacy:										
Reporting Your Pain - patient education brochure ⁷	X	X	X		X	X	X	X	X	
LBPI NRS ⁸	X	X	X		X	X	X	X	X	X
Roland Morris Disability Questionnaire			X		X	X	X	X	X	X
Patient Global Assessment LBP	X		X		X	X	X	X	X	X
MOS Sleep Scale Survey			X		X	X	X	X	X	X
SF-36			X		X	X	X	X	X	X
EQ-5D-5L			X		X	X	X	X	X	X
Safety:										
Weight	X								X	X
Vital Signs ⁹	X	X	X		X	X	X	X	X	X
Physical Examination ¹⁰	X								X	X
Electrocardiogram	X								X	X
Joint Pain Questionnaire	X		X		X	X	X	X	X	X
Event-triggered imaging ¹¹					X	X	X	X	X	X
Orthostatic blood pressure	X	X	X		X	X	X	X	X	X
Survey of autonomic symptoms	X		X			X	X	X	X	X
Neurologic examination	FULL		BRIEF		BRIEF	BRIEF	BRIEF	BRIEF	FULL	FULL
SC injection site evaluation			X			X	X	X		
Adverse Events	X	X	X	X	X	X	X	X	X	X
Pre-op questionnaire (TJR) ¹²										X
Laboratory Testing:⁶										
Hematology	X		X			X	X	X	X	X

Study Week	Screening Period	Pre-Randomization Period	Treatment						End of Treatment Period	Treatment Period Early Termination Visit
			1	2	4	8	12	16		
Study Day (visit window)	up to -37 to -8	-7 (+3) Pre-Rand Visit	1 Baseline	8 (±1)	15 (±3)	29 (±7)	57 (±7)	85 (±7)	113 (±7)	ET
Visit Number	1	2	3	Ph call 1	4	5	6	7	8	ET
Blood Chemistry	X		X			X	X	X	X	X
HbA1c	X									
FSH and estradiol ¹³	X									
Pregnancy test (WOCBP) ¹⁴	SERUM		URINE		URINE	URINE	URINE	URINE	SERUM	SERUM
Urinalysis/Urine Creatinine and Phosphorous	X		X			X	X	X	X	X
PK/Drug Concentration and ADA Samples:⁶										
PK/Drug conc. Sample			X		X	X	X	X	X	X
ADA sample			X						X	X
Genomics sub-study sample ¹			X							
Research serum/plasma sample			X		X	X	X	X	X	X

1. Only for patients who provide written informed consent for the optional genomics sub-study. The sample should be collected at the baseline visit, but may be collected at any subsequent visit during the study.
2. If screening radiographs are inconclusive for potential joint-related findings, an MRI of the affected joint must be performed and assessed by the central reader. After the patient has otherwise met study eligibility criteria assessed during the screening period, an MRI of any knee or hip joint that has a baseline K-L score of ≥ 3 must be performed prior to the pre-randomization visit. Confirmation that the image has been accepted and confirmed query-free by the central reader must be received by the site before the pre-randomization visit. Confirmation from the central reader that there are no exclusionary findings on MRI must be received from the central reader before a patient can be randomized.
3. A lumbar spine AP/Lateral should be obtained if the MRI of the lumbar spine shows evidence suggestive of a destructive or unstable process.
4. Early Termination: Imaging assessments (X-rays of the knees, hips, and shoulders, and MRI) need to be repeated only if it has been >30 days since the joint was last imaged. If it has been ≤ 30 days since imaging assessments were completed, imaging assessments may be completed at the discretion of the investigator.
5. Patients will be trained on using the EDiary after initial patient eligibility has been confirmed during the screening period. Patients will use the EDiary to report their daily NRS LBP score and daily use of paracetamol/acetaminophen through the week 16 visit.
6. Study drug administration will be the last procedure at each dosing visit, and will be done after all laboratory samples have been collected and all study assessments and procedures are performed including blood draws for drug concentration and ADA. At the day 1 and week 8 visits, patients will receive the SC injection first, followed by the IV infusion. After IV administration of study drug, patients will be observed in the clinic for approximately 2 hours for evidence of a hypersensitivity reaction, and for 1 hour after SC dosing.

7. At the screening and pre-randomization visits, study staff will review the "Reporting Your Pain" brochure with the patient to ensure the patient understands how to report pain accurately. At subsequent clinic visits patients will be asked to review the "Reporting Your Pain" brochure themselves. At the screening visit, study staff will also review with the patient the "Participating in a Research Study: What You Need to Know" brochure.
8. Low back pain intensity NRS score will be recorded by the site at the screening visit and at the pre-randomization visit, and by the patient each day (at approximately 6:00 PM) using the EDiary, starting during the pre-randomization period through week 16.
9. If the pulse is less than 45 bpm at any visit after the randomization visit, an ECG with rhythm strip will be obtained and sent to the central reader to confirm the heart rate and rhythm.
10. The physical examination should include an exam of the knee, hip, and shoulder joints.
11. Imaging (X-ray and/or MRI) will be considered for worsening joint pain, despite treatment with analgesics, which is inconsistent with the normal progression of OA and lasts for at least 2 weeks (or less, at the discretion of the investigator).
12. In the event that a patient must undergo TJR surgery during the study, the patient will complete the early termination visit and the procedures outlined in the schedule of events for TJR follow-up (Table 3). The early termination visit should be completed before TJR surgery if at all possible. TJR questionnaires are Knee Society Score questionnaire for knee replacements or Harris Hip Score questionnaire for hip replacements.
13. To be performed only if postmenopausal status has to be assessed for female patients ≤ 59 years of age.
14. In the event of a positive urine pregnancy test result, the patient must have a serum pregnancy test with a negative result in order to continue study participation. If the serum pregnancy test is positive, the patient must be withdrawn from study drug and should be asked to return to the clinic for all remaining study visits on the visit schedule. (see Section 5.2.2)

Table 2 Schedule of Events – Follow-up Period

Table 2: Schedule of Events – Follow-up Period – Week 20 through Week 36

Study Week	Follow-up Period				End of Study	Follow-up Period
	Week 20	Week 24	Week 28	Week 32	Week 36	Early Termination
Study Day (visit window)	141(±7)	169(±7)	197(±7)	225(±7)	253(±7)	
Visit Number	9	Ph call 2	Ph call 3	Ph call 4	10	ET
Treatment:						
Concomitant Meds	X	X	X	X	X	X
Efficacy:						
Reporting Your Pain - patient education brochure ¹	X					
LBPI NRS	X				X	X
Roland Morris Disability Questionnaire	X				X	X
Patient Global Assessment LBP	X				X	X
MOS Sleep Scale Survey	X				X	X
SF-36	X				X	X
EQ-5D-5L	X				X	X
Safety:						
Vital Signs ²	X				X	X
Physical Examination					X	X
Electrocardiogram					X	X
Joint Pain Questionnaire	X				X	X
Event-triggered imaging ³	X				X	X
Orthostatic blood pressure	X				X	X
Survey of autonomic symptoms	X				X	X
Neurologic examination	BRIEF				FULL	FULL
Adverse Events	X	X	X	X	X	X
MRI of any knee or hip with baseline K-L ≥3 ⁴					X	X ³
Pre-op questionnaire (TJR) ⁵						X
Laboratory Testing:						
Hematology					X	X
Blood Chemistry					X	X
Pregnancy test (WOCBP)	URINE				SERUM	SERUM
Urinalysis/Urine Creatinine and Phosphorous					X	X

Study Week	Follow-up Period				End of Study	Follow-up Period Early Termination
	Week 20	Week 24	Week 28	Week 32	Week 36	
Study Day (visit window)	141(±7)	169(±7)	197(±7)	225(±7)	253(±7)	
Visit Number	9	Ph call 2	Ph call 3	Ph call 4	10	ET
PK/Drug Concentration and ADA Samples:						
PK/Drug conc. sample	X				X	X
ADA sample					X	X
Research serum/plasma sample					X	X

1. The patient will be asked to review the "Reporting Your Pain" brochure themselves.
2. If the pulse is less than 45 bpm at any visit after the randomization visit, an ECG with rhythm strip will be obtained and sent to the central reader to confirm the heart rate and rhythm.
3. Imaging (X-ray and/or MRI) will be considered for worsening joint pain, despite treatment with analgesics, which is inconsistent with the normal progression of OA and lasts at least 2 weeks (or less, at the discretion of the investigator)
4. Imaging assessments (X-rays of the knees, hips, and shoulders, and MRI) need to be repeated only if it has been >30 days since the joint was last imaged. If it has been ≤30 days since imaging assessments were completed, imaging assessments may be completed at the discretion of the investigator.
5. In the event that a patient must undergo TJR surgery during the study, the patient will complete the early termination visit and the procedures outlined in the schedule of events for TJR follow-up (Table 3). The early termination visit should be completed before TJR surgery if at all possible. TJR questionnaires are Knee Society Score questionnaire for knee replacements or Harris Hip Score questionnaire for hip replacements.

Table 3 Schedule of Events – Follow-up for Patients who undergo Total Joint Replacement Surgery

Table 3: Schedule of Events - Follow-up for Patients Who Undergo Total Joint Replacement Surgery

Follow-up Study Day (Visit Window)	Follow-up Period ¹	
	Post-Operative Follow-up Visit 1 4 weeks after the date of the joint replacement surgery F/U Day 29 (±7)	Long-Term Follow-up Visit 2 20 weeks after the date of the joint replacement surgery F/U Day 140 (±7)
Treatment:		
Concomitant medications	X	X
Safety:		
Vital signs	X	X
Physical examination with joint exam	X ¹	X
Medical history related to the total joint replacement	X	X
Joint pain questionnaire	X	X
Post-operative assessment questionnaire ²	X	X
Event-triggered imaging ³	X	X
MRI of any knee or hip with a baseline K-L ≥3		X

1. Relevant information related to the surgery should be collected, including placement of the prosthesis and healing of the surgical wound.
2. Formal post-operative assessment of joint replacements will be done by completing the Knee Society Score questionnaire for knee replacements or the Harris Hip Score questionnaire for hip replacements. Full details of these assessments are provided in the study reference manual.
3. Imaging (X-ray and/or MRI) will be considered for worsening joint pain, despite treatment with analgesics, which is inconsistent with the normal progression of OA and lasts at least 2 weeks (or less, at the discretion of the investigator).

